## **14.2 Serious Adverse Events**

Serious Adverse Events will be summarised by system organ class and preferred term.

A listing of the reasons for considering a serious adverse event will be provided.

## **14.3 Other Safety Measures**

### **14.3.1 Clinical Laboratory Evaluations**

All laboratory values of potential clinical importance will be listed.

### **14.3.2 Vital signs**

Vital signs evaluation pre- and post-scan at the scanning visit will be summarised by group.

Vital signs of potential clinical importance will be listed.

### **14.3.3 Physical examination**

Abnormal physical examination findings will be listed by group.

## **14.4 Positron Emission Tomography**

Positron Emission Tomography (PET) parameters will be summarised using the safety population.

Each PET parameter ( $V_T$  and mean SUV) will be listed and summarised by region and group.

A Bayesian approach to the analysis of the PET parameters will be used.

For any important endpoint, we describe our uncertainty concerning its true value with a probability density function,  $p(\theta)$ , say. (Suppose ‘ $\theta$ ’ represents Volume of Distribution, derived from the PET and blood sample data. The following argument will apply to any such endpoint which takes numerical values on the real line.) Pre-study start, we will characterise  $p(\theta)$  in such a way that our “prior belief” about the true endpoint’s value is entirely diffuse over the real line (this approach implies that all conclusions about the endpoint are driven only by the data gathered in the study).

We will gather evidence about the endpoint in the data from the study, which we will characterise via its likelihood function (derived from the relevant sampling distribution,  $l(x|\theta)$ , say, where ‘ $x$ ’ stands for ‘data’). From the likelihood function the usual summary statistics for the endpoint are derived.

It is highly likely, based on similar PET studies, that a Normal likelihood function will be suitable. This will have an unknown mean and known variance taken from the raw data (i.e.

$x_j \sim N(\theta_j, \sigma_j^2)$  where  $j$  is the PAH patient group or the HV group). An uninformative conjugate Normal prior density function with mean zero and a vast variance will be adopted for the group mean ( $P(\theta_j) = N(0, \sigma_{0,j}^2)$ ) leading to the standard Normal posterior density functions for the endpoints of interest (Should the data not support a Normal likelihood function, alternative parametric forms, such as a log-Normal density, will be investigated). In order for the prior to be sufficiently non-informative, the variance of the prior will be approximately 100 times the variance of the data.

We will apply Bayes' theorem to derive the posterior density function  $p(\theta_j | x_j)$ . We will use PROC MCMC in SAS. The number of burn-in iterations will be at least 10,000 and the number of MCMC iterations, excluding the burn-in iterations will be at least 5000. These samples may be thinned if autocorrelation is high. An example of the SAS code for a normal likelihood function is given below:

```
ods output PostSummaries = PostSummaries PostIntervals = PostIntervals  
PosteriorSample = PosteriorSample;  
  
PROC MCMC data = BayesianTest nmc = 5000 nbi = 10000 monitor=(_parms_ muratio);  
parms mu1 mu2;  
muratio = mu1/mu2;  
  
MODEL PAH ~ norm(mu1, sd = 1);  
  
MODEL HVs ~ norm(mu2, sd = 1);  
  
prior mu1 mu2 ~ normal(0, sd = 100);  
  
preddist outpred = BayesianPred nsim = 5000 covariates = PredCovariates;  
by endpoint region;  
  
run;
```

The posterior distribution for each endpoint will be summarised by region and group, including the mean, median, SD, interquartile range and 95% credible interval based on the highest posterior density (HPD) interval.

Samples from the posterior distribution for the group mean  $p(\theta_j|x_j)$  for the PAH patients and for the HV subjects will be used to determine the posterior distribution for the ratio of group means (PAH patients to HV subjects). The posterior distribution for the ratio of group means

will be summarised by region and endpoint. Plots of the median and 95% credible interval for the posterior distribution of the group mean and the ratio of group means will be presented for each endpoint and region. Individual subject data will also be included on the plot using a different symbol for each match pairs of subjects. Each plot will also include the posterior distribution of the ratio of the group means.

Samples from the posterior distribution of the ratio of group means will be used to determine the probability that the ratio of the endpoint in PAH patients to HV subjects exceeds 1 for each endpoint and region. This will be repeated for other values to allow us to plot to provide a graph of the “probability that this ratio exceeds a certain value, plotted against ratio, for ratios in the range 0.5 to 2 will be presented for each endpoint and region.

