#### **4.4. Design Justification**

The study will be open-label and non-randomised as there is no intention of performing inference about the safety or efficacy profile of an NCE or other test therapeutic vs any form of control. A sufficient number of subjects will be recruited, based on feasibility, to permit adequate quantification of the uptake of [C]-GSK2256098 in target organs within the patient population, and those levels of expression will be compared with those measured in a set of age and gender-matched healthy controls. This form of case matching is intended to reduce the variance in the estimate of uptake by imposing a form of biological control on the signal derived from the subjects.

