### 9.4. Key Elements of Analysis Plan

#### 9.4.1. Primary Analyses

For any important endpoint, we describe our uncertainty concerning its true value with a probability density function,  $p(t)$ , say. (Suppose ‘ $t$ ’ represents Volume of Distribution, derived from the PET and blood sample data. The following argument will apply to any such endpoint which takes numerical values on the real line.) Pre-study start, we will characterise  $p(t)$  in such a way that our “prior belief” about the true endpoint’s value is entirely diffuse over the real line (this approach implies that all conclusions about the endpoint are driven only by the data gathered in the study.)

We will gather evidence about the endpoint in the data from the study, which we will characterise via its likelihood function (derived from the relevant sampling distribution,  $l(x|t)$ , say, where ‘ $x$ ’ stands for ‘data’) From the likelihood function are derived the usual summary statistics for the endpoint.

It is highly likely, based on similar PET studies, that a Normal likelihood function will be suitable (that is will provide a reasonable fit to the observed data.) A conjugate Normal prior density function with mean zero and a vast variance will be adopted, leading to the standard Normal posterior density functions for the endpoints of interest. (Should the data not support a Normal likelihood function, alternative parametric forms, such as a log-Normal density, will be investigated.)

We will apply Bayes’ theorem to derive the (constantly evolving) posterior density function  $p(t | x)$ , and use this to produce the following quantities of inferential interest:

- What is currently (as a function of accruing data) the most probable true value of the endpoint? These point estimates, given the vagueness of the prior density, will be both the maximum likelihood, and the Bayesian maximum a posteriori, estimates of the parameters (the true values of the endpoints.)
- What is a range of plausible values for the true value of the endpoint, such that there is a 95% chance that the true value lies within that range? These intervals will be the 95% highest posterior density intervals for each parameter.

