- What is the probability that the ratio of the endpoint in patients compared to the endpoint in HVs exceeds one, given the current data? Similarly, we will derive the 95% highest posterior density range for that ratio. Since the ratio of two Normally-distributed endpoints will not itself be Normally distributed, it is likely that some

simple Monte Carlo Markov Chain methods will be applied to derive these point and interval estimates.

- What does the graph of “probability that this ratio exceeds x”, plotted against x, look like, for x in the range 0.5 to 2 (say – other ranges may be explored as data permits)?
- Given the current sample size, how likely, were we to recruit a further n patients, are those estimates to change substantially, for n in the range 2, 4, 6...up to a maximum sample size of 12. For this question, we will derive the predictive posterior density function for the ratio.

Full details of these approaches will be provided in the RAP.

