## **8.1 Sample Size Re-estimation or Adjustment**

The first statistical evaluation of the data will occur once five patients and five healthy volunteers have been studied in the PET scanner, and the relevant functional endpoints (such as  $V_T$ ) have been derived from their scan data by Imanova scientists. At this point, the statistical analysis (set out below) will be carried out, and, based on those results, the team may decide to recruit more subjects, up to a total of twelve patients and twelve healthy volunteers.

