**Template T\_PT2\_GK**

Table 14.3.6.xx Summary of the Posterior Distribution for Volume of Distribution ( $V_T$ ) and Mean Standardised Uptake Values (SUV), by Group and Region

Parameter	Region	Group	Prior Distribution for $\Theta$	Value of $\sigma$ used in the model	Posterior distribution $P(\Theta x)$				
					Mean	SD	Median	25th quartile	75th quartile
Mean SUV	Heart Chamber	PAH Patients (N=xx)	normal(0, sd = 100)	1					
		Healthy Volunteers (N=xx)	normal(0, sd = 100)	1					
	Whole Lung								

Number of MCMC iterations, excluding the burn-in iterations = 5,000. Number of burn-in iterations = 10,000

The PET parameters are assumed to follow a normal distribution with unknown mean  $\Theta$  and known variance  $\sigma^2$  (i.e.  $N(\Theta, \sigma^2)$ )

$P(\Theta|x)$  is the posterior distribution for  $\Theta$  given the PET data  $x$ . 95% credible intervals based on the highest posterior density interval.

Mean SUV is calculated over a xx minute period

Source: Listing 16.2.xx

Programming notes: Continued with all end points, regions and groups. Replace xx with the time period in the footnote .

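### SAP 14.4 treats a variance estimated from 5 to 12 subjects per group as known, so the group-mean 95% intervals cover only 87.8% (n=5) to 92.4% (n=12)

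*SAP*

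**What the plan says.** Protocol 9.4.1 plans a Normal likelihood with a diffuse Normal prior and asks for a range of plausible values "such that there is a 95% chance that the true value lies within that range", to be given by 95% HPD intervals. It does not call the variance known.

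The SAP adds that assumption in three places:

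- **SAP 14.4, text.** On the Normal likelihood: "This will have an unknown mean and known variance taken from the raw data". This is done separately for PAH patients and healthy volunteers. The prior for each group mean is centred at zero, with variance about 100 times that of the data.
- **SAP 14.4, example code.** "MODEL PAH ~ norm(mu1, sd = 1" enters the SD as a constant. The PARMS statement lists only the two means, and no prior is given for an SD. The value 1 is a placeholder and nothing below depends on it. The predictive draws come from the same model: "preddist outpred = BayesianPred nsim = 5000 covariates = PredCovariates".
- **SAP 16.3.1, template T_PT2_GK.** A column reports the sigma used. The footnote begins "The PET parameters are assumed to follow a normal distribution with unknown mean" and goes on to call the variance known.

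Neither document gives a prior for sigma, a t posterior or a small-sample correction. On timing, SAP 8.1 says: "The first statistical evaluation of the data will occur once five patients and five healthy volunteers have been studied". The maximum is twelve per group.

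**The concern.** An SD estimated from five subjects is itself very uncertain. Fixing it at its estimate removes that uncertainty from every interval and probability computed from it, and the effect is largest at the smallest sample size.

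The study does no hypothesis testing, so these posterior summaries are its inference. The group-mean interval is a planned output: SAP 14.4 says it will be summarised and plotted by region and group. The ratio of means, the probability that it exceeds a given value, and the predictive draws carry the same fixed SD. The protocol uses the predictive density to ask how far estimates might move with more recruitment: "For this question, we will derive the predictive posterior density function for the ratio". The first look, at five per group, is when the team chooses between stopping and recruiting more.

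**Working it through.** **Inputs.** n=5 per group at the first look (SAP 8.1) and at most 12 (SAP 8). Variance fixed at s², prior for the mean N(0, 100 s²), 95% HPD interval (SAP 14.4). I take s² as the usual sample variance with divisor n−1.

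**Posterior for a group mean.** Its precision is n/s² + 1/(100 s²). At n=5 the weight on the sample mean is 500/501 = 0.998, and the posterior SD is s√(100/501) = 0.4468 s, against s/√5 = 0.4472 s. The prior hardly matters, so the interval is x̄ ± 1.96 s/√n.

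**The plan's own figure.** If sigma really were known, the level would be P(|Z| < 1.96) = 95.0%. The stated 95% is reproduced only on that assumption.

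**With s from the same subjects.** (x̄ − μ)/(s/√n) follows t with n−1 df, so coverage is P(|t(n−1)| < 1.96):

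| n | t multiplier for 95% | needed width ÷ planned width | coverage as planned |
|---|---|---|---|
| 5 | 2.776 | 1.42 | 87.8% |
| 6 | 2.571 | 1.31 | 89.3% |
| 7 | 2.447 | 1.25 | 90.2% |
| 8 | 2.365 | 1.21 | 90.9% |
| 9 | 2.306 | 1.18 | 91.4% |
| 10 | 2.262 | 1.15 | 91.8% |
| 11 | 2.228 | 1.14 | 92.2% |
| 12 | 2.201 | 1.12 | 92.4% |

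Simulation of the SAP posterior (1,000,000 trials per setting, CVs of 10% to 50%) gave 87.9% at n=5 and 92.4% at n=12. Prior variances of 100 and 10,000 times the data variance gave the same result; the second is the ratio implied by the example code (SD 100 against SD 1). HPD intervals from 5,000 draws gave 87.5% and 92.3%. With divisor n in the variance, coverage would be lower: 84.6% and 91.3%.

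This is not only a frequentist reading. Under the reference prior for sigma, the posterior for the mean is t with n−1 df, so the planned interval holds 87.8% posterior probability at n=5.

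**Prediction of one new subject.** (x_new − x̄)/(s√(1+1/n)) is also t(n−1), so with sd fixed at s the coverage is again 87.8%, 90.9% and 92.4% at n=5, 8 and 12.

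**Ratio of means.** There is no closed answer without the CV in each group and the within-pair correlation ρ. The documents give neither, so both are assumptions here. Simulated coverage of the planned 95% HPD interval for the ratio (true ratio 1.0 and 1.5; 8,000 trials per cell, 4,000 draws each):

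| Setting | ρ=0 | ρ=0.3 | ρ=0.5 |
|---|---|---|---|
| n=5, equal CVs of 15–35% | 91.3–92.6% | 94.8–95.5% | 96.9–97.6% |
| n=5, CVs 45% and 15%, either way round | 89.1–91.1% | 91.7–93.1% | 92.9–94.3% |
| n=12, equal CVs | 93.1–93.9% | 96.7–97.4% | – |

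Coverage rises with ρ because the planned ratio treats the groups as independent. Protocol 4.4 says of the matching: "This form of case matching is intended to reduce the variance in the estimate of uptake". If it succeeds, the ratio's true variance is smaller than the model assumes, which can offset the fixed SD.

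**The case against.** The strongest reply is that the comparison of interest is PAH against healthy volunteers. The stopping options concern that difference, and no passage ties stopping to a group-mean interval. For the ratio the shortfall is conditional: with similar CVs and ρ of about 0.3, the planned interval is close to 95% and the fix moves it further away. As an illustration, take a cut-off of 0.975 for the probability that the ratio exceeds 1 (the documents set none). With n=5, CVs of 25% and a true ratio of 1, the planned model passes it in about 4.3% of trials at ρ=0 and 2.4% at ρ=0.3, against a nominal 2.5%. With sigma estimated the figures are 1.6% and 0.5%. The fix also leaves the pairing unmodelled.

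Much of this stands. The 87.8% must not be carried over to the ratio, and no false-stop rate can be claimed. The single-subject predictive figure shows the mechanism but is not the protocol's predictive quantity, which is for the ratio. All coverages are at fixed n, whereas the final n depends on the data.

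It does not rescue the group-mean intervals, which are too narrow whatever ρ is. Any offset in the ratio comes from two omissions happening to cancel. With clearly unequal CVs the ratio interval stays below 95% at n=5 for every ρ tried.

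**Conclusion.** The concern holds and should be fixed. For a Normal endpoint with the n−1 variance and fixed n, the planned 95% group-mean intervals cover 87.8% at n=5, rising to 92.4% at n=12. This needs no outside input.

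For the ratio the conclusion is conditional on assumed CVs and ρ. The interval is too narrow if pairs are uncorrelated or, at n=5, if the CVs differ clearly. It can reach or exceed 95% if the CVs are similar and ρ is about 0.3 or more.

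**What to change.** In SAP 14.4 and the code, make each group's SD a parameter with a vague prior, for example p(σ_j) ∝ 1/σ_j. Keep the Normal likelihood and the ratio of group means, and use this one model for the group means, the ratio, the exceedance probabilities and the predictive draws. In T_PT2_GK, replace the column for the sigma used, and the known-variance wording in the footnote, with a posterior summary of σ_j.

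Keep the prior variance of the mean as a fixed number, as now. Group-mean coverage at n=5 is then 95.0–95.6%. If that prior were instead scaled to the unknown σ_j, coverage at n=5 would be 94.5%, 92.9% and 92.4% for CVs of 15%, 25% and 35%.

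The work is one SAP sentence, PARMS and PRIOR statements for two SDs, and one column and footnote. Group-mean intervals widen by a factor of 1.42 at n=5 and 1.12 at n=12. The ratio interval becomes conservative. At n=5 with equal CVs it covers 97.5–98.0% at ρ=0 and 98.7–98.9% at ρ=0.3; with CVs of 45% (PAH) and 15% (HV) it covers 96.2–96.5% at ρ=0. At n=12 with equal CVs it covers 95.8–96.6% at ρ=0 and 98.2–98.5% at ρ=0.3.

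A log-scale model with a common SD is optional only. It changes the estimand to a ratio of geometric means and assumes equal variances.

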#### 5.1. Inclusion Criteria

##### 5.1.1. Healthy Volunteers

A subject will be eligible for inclusion in this study only if all of the following criteria apply:

AGE

 
Healthy subjects enrolled between 40 to 70 years inclusive at the time of signing the informed consent. Healthy subjects will be recruited to be age (<math>\pm</math> 5 years) and gender matched to PAH patients.
 

TYPE OF SUBJECT AND DIAGNOSIS INCLUDING DISEASE SEVERITY

 
Healthy as determined by the investigator or medically qualified designee based on a medical evaluation including medical history, physical examination, laboratory tests and cardiac monitoring.
 
Normal spirometry at Screening (FEV1 and FVC <math>\geq</math> 80% of predicted – measurements to be taken in triplicate and the highest value must be <math>\geq</math> 80% of predicted).
 
A subject with a clinical abnormality or laboratory parameter(s) outside the reference range for the population being studied may be included only if the investigator, in consultation with the medical monitor if deemed necessary, agree and document that the finding is unlikely to introduce additional risk factors and will not interfere with the study procedures.
 
Subject is ambulant and capable of attending for PET-CT imaging.
 
A negative Allen's test in at least one arm for arterial blood sampling (indicating adequate collateral circulation to the hand from both the radial and ulnar arteries).
 

WEIGHT
7. Body weight $\geq$ 50 kg and body mass index (BMI) within the range 18.5 – 35 kg/m  (inclusive).

SEX

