## **13.2 Protocol Deviations**

Before closing the database, data listings will be reviewed to identify any significant deviations and determine whether the data should be excluded from any analysis populations.

Major protocol deviations include subjects who:

- Entered the study even though they did not satisfy the entry criteria.
- Met the criteria for withdrawal from the study but were not withdrawn.
- Received the wrong treatment or incorrect dose.
- Received an excluded concomitant therapy.
- Received investigational product(s) past the expiration date.
- Healthy volunteers who are not matched to a PAH patient on gender or with age not within  $\pm 5$  years

A summary table of the important deviations will be provided.

A listing of inclusions/ exclusion deviations will be provided.

A listing of all important deviations will be provided.

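### SAP 14.4 treats the group variances as known and ignores the matching, so the 95% interval for the PAH/HV ratio and P(ratio > 1) are miscalibrated in two opposing ways

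*SAP*

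**What the plan says.** **Design.** Protocol 5.1.1, criterion 1: "Healthy subjects will be recruited to be age" (within 5 years) and gender matched to the patients. Protocol 4.4 gives the purpose: "This form of case matching is intended to reduce the variance in the estimate of uptake". Protocol 9.2 and SAP 8 start with five patients and five volunteers and then add patient-volunteer pairs, up to twelve per group. SAP 13.2 counts as a major deviation "Healthy volunteers who are not matched to a PAH patient on gender or with age not within" 5 years.

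**Analysis.** SAP 14.4 gives each group its own Normal likelihood. On the variance: "This will have an unknown mean and known variance taken from the raw data". Each group mean has its own vague Normal prior, and draws of the two means "for the PAH patients and for the HV subjects will be used to determine the posterior distribution for the ratio of group means". The example PROC MCMC code has one univariate statement per group, for instance "MODEL HVs ~ norm(mu2, sd = 1"), with nothing linking them. The footnote to template T_PT2_GK repeats the assumption: "The PET parameters are assumed to follow a normal distribution with unknown mean" and known variance.

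**Use of the result.** Protocol 9.4.1 asks, as data accrue: "What is the probability that the ratio of the endpoint in patients compared to the endpoint in HVs exceeds one, given the current data"? It also asks for the 95% highest posterior density range of the ratio.

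**Use of the pairs.** In the SAP, pair identity appears only in the age-difference summary (13.3), the plot symbols (14.4 and template F_PT1_GK) and the deviation check (13.2).

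**The concern.** The sample is 5 to 12 per group, and the ratio posterior is the evidence on which recruitment stops or continues. Its spread should reflect what the data support. Two features of the model prevent this, and they act in opposite directions.

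- A variance estimated from five values carries real uncertainty. Entering it as known removes that uncertainty, so the interval is too short and P(ratio > 1) too extreme.
- If matched subjects resemble each other in uptake, the two sample means are positively correlated and their contrast is more precise than independent groups imply. The likelihood and prior factorise by group, so the posterior covariance of the two means is zero whatever the data show. Any precision gained from matching is left out of the reported interval.

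Whether the nominal 95% is achieved therefore depends on two unrelated errors happening to offset.

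**Working it through.** **Inputs.** From the documents: n = 5 at the first look and 12 at most, 1:1; plug-in variances; prior variance about 100 times the data variance. Not in the documents, so assumed: within-pair correlation rho from 0 to 0.5, and equal SDs unless stated. The plan gives no coverage, power or correlation figure to reproduce.

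**Scale.** Coverage is worked on the difference of means. When the HV mean is well above zero, the ratio exceeds 1 exactly when the difference exceeds 0, so this scale carries over to P(ratio > 1). The prior hardly matters: shrinkage is n/(n + 0.01) = 5/5.01 = 0.998 at n = 5.

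**Step 1, known variance alone (rho = 0).** The plug-in standard error is sqrt((s1² + s2²)/n). At equal n this equals the pooled standard error, so the standardised difference is t on 2n − 2 df but is referred to 1.96.

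- n = 5: P(|t8| < 1.96) = 91.4%
- n = 12: P(|t22| < 1.96) = 93.7%

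**Step 2, ignored pairing alone.** With k the ratio of the two CVs, the interval is too wide by the factor sqrt((1 + k²)/(1 + k² − 2·rho·k)).

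| rho | k = 1 | k = 2 |
|---|---|---|
| 0.1 | 1.054 | 1.043 |
| 0.3 | 1.195 | 1.147 |
| 0.5 | 1.414 | 1.291 |

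**Step 3, both errors as planned.** Coverage of the nominal 95% interval, 200,000 simulated trials per cell:

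| rho | 5 pairs | 12 pairs |
|---|---|---|
| 0 | 91.4% | 93.7% |
| 0.1 | 92.7% | 94.9% |
| 0.3 | 95.2% | 97.0% |
| 0.5 | 97.2% | 98.8% |

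The errors cancel near rho 0.3 at 5 pairs and near 0.1 at 12.

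**Step 4, pairing without correcting the variance.** A paired interval with known variance covers P(|t4| < 1.96) = 87.8% at 5 pairs and P(|t11| < 1.96) = 92.4% at 12. Pairing must come with an estimated variance.

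**Step 5, cost of pairing with estimated variances.** Mean interval width at 5 pairs and rho 0, in SD units:

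| Interval | Mean width | Coverage |
|---|---|---|
| SAP plug-in | 2.40 | 91.4% |
| Pooled t, 8 df | 2.83 | 95.0% |
| Welch | 2.93 | 95.6% |
| Paired, prior \|Sigma\|^-2 (4 df) | 3.30 | 95% |
| Paired, prior \|Sigma\|^-3/2 (3 df) | 4.37 | 97.9% |

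The last row follows from the one above: 3.30 × (3.182/2.776) × sqrt(4/3) = 4.37. At rho 0 the first paired interval is 3.30/2.93 = 1.13 times the Welch width and 3.30/2.83 = 1.17 times the pooled width; the ratio of t quantiles alone is 2.776/2.306 = 1.20. Break-even with the pooled interval is at rho = 1 − (t(2n−2)/t(n−1))²:

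- n = 5: 1 − (2.306/2.776)² = 0.31
- n = 12: 1 − (2.074/2.201)² = 0.11

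**Step 6, plausible rho.** With ages uniform on 40–70 and volunteers within 5 years, the within-pair age correlation is about 0.94. Rho 0.1 then needs age and gender to explain about 10–11% of uptake variance in both groups (0.1/0.94 = 0.106), and rho 0.3 about 30–32% (0.3/0.94 = 0.319). Five pairs cannot settle the question: an observed r of 0.5 has a Fisher 95% interval from −0.68 to 0.96.

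**The case against.** The strongest reply is that the pairing half may be negligible. Rho is not given, age is restricted to 40–70, and at rho 0.1 ignoring the pairs changes the width by only 5%. Ignoring a positive rho errs on the cautious side. At 5 pairs a paired model estimates the variance on 4 df and can be wider than an unpaired one; with the |Sigma|^-3/2 prior it is much wider. All of this stands, and it is why the paired model is proposed as an addition and not as the required primary. It does not defend the known variance, which under-covers at rho 0.

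It can also be said that Protocol 4.4 speaks of biological control and not of a paired analysis, and that Protocol 9.4.1 is itself group-wise. That is correct. The SAP does not depart from the protocol here; both leave out the precision that 4.4 names as the aim.

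Four stronger readings are tempting and are not supported:

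- *The SAP has no rule for a dosed subject without a match.* It has one. SAP 9 analyses everyone dosed, SAP 12.1 keeps withdrawals, and the group-wise model in 14.4 needs no partner. A rule is needed only for an added paired analysis.
- *Independent groups with estimated variances would be too wide even at rho 0.* That depends on the prior. Separate 1/sigma priors give 97.6% at 5 pairs, but a Welch interval, also with separate variances, gives 95.6%.
- *The matching is wasted.* It still balances age and gender, and any real gain in precision still occurs; the reported interval does not show it.
- *The example code fixes every SD at 1.* The code is labelled an example, and the text takes the variances from the data.

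**Conclusion.** The point holds. As written, the ratio's interval and P(ratio > 1) carry two opposing errors. The known-variance error is certain in direction and does not depend on the matching: 91.4% coverage at 5 pairs and 93.7% at 12 when rho is 0. The pairing error is structural, but its size is unknown: 5%, 20% or 41% excess width at rho 0.1, 0.3 or 0.5 with equal CVs, and less with unequal CVs. A negative rho would reverse its direction. Together they give about 91–97% coverage at 5 pairs and 94–99% at 12 for rho between 0 and 0.5. These figures rest on Normal data, equal SDs and the difference scale.

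A reader might infer that a stop-or-continue decision would change. That cannot be shown, because neither document sets a numerical threshold for stopping. Estimating the variances is a plain correction. A pre-specified paired analysis is a cheap addition. Whether it should be primary at five pairs is a judgement for the sponsor.

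**What to change.** Amend SAP 14.4 before the first look:

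1. **Primary model.** Estimate the group variances, with stated priors, instead of plugging in sample values. State whether the variances are separate or pooled. Change template T_PT2_GK, which prints a fixed sigma, to show the estimated SDs.
2. **Added paired analysis.** Fit a bivariate Normal to the matched pairs with both SDs and the correlation estimated, and take mu1/mu2 from the joint draws so that the target stays the ratio of group means. State and justify the covariance prior, since at 5 pairs the choice between |Sigma|^-2 and |Sigma|^-3/2 moves the mean width from 3.30 to 4.37 SD. Do not carry the known variance into this model.
3. **Unmatched subjects in the paired analysis.** Say whether they are left out or enter with the partner value missing.
4. **Primary status.** State in advance which analysis is primary and why, and do not choose from the observed correlation.

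The cost is SAP wording, priors, a revised MCMC model and one template edit. The pair link is already needed for the age-matching table and the plots, and the example code already reads both groups from one data set. The statistical cost falls only on a paired primary analysis: at 5 pairs and rho 0 it is about 13% wider than Welch and 17–20% wider than pooled, breaking even with pooled near rho 0.31 at 5 pairs and 0.11 at 12.
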